## 219111 (EPI-ZOSTER-097 VE US DB) Protocol Final

Drug	NDCs
	55700053930, 55700065130, 55700066335, 55700066415, 55700066435, 55700066440, 55700066460, 55700078635, 55812038401, 55812038402, 55812038403, 55887024615, 55887024621,
	55887024625, 55887024630, 55887024640, 55887024650, 55887085325, 55887085330, 55887085350, 55887085360, 55887085390, 55887097730, 55887097740, 57866695002, 57866695003,
	57866695004, 57866695005, 57866695103, 58016011100, 58016011115, 58016011120, 58016011125, 58016011130, 58016011160, 58016011190, 58016011200, 58016011220, 58016011230,
	58016011260, 58016011290, 58016062700, 58016062720, 58016062720, 58016062730, 58016062760, 58016062790, 58118894303, 58118894304, 58118894308, 58118894703, 58118894703, 58597806703,
	58597806704, 58597806706, 58597806707, 58597806708, 58864019125, 58864019135, 58864060201, 58864060230, 58864087635, 59911316305, 60429001201, 60429001205, 60429030901,
	60429030905, 60429030910, 60429031001, 60429031005, 60429071101, 60429071105, 60429071150, 60429071201, 60429071205, 60429071301, 60429071305, 60429071350, 60429091101,
	60429091105, 60505004206, 60505530601, 60505530608, 60505530701, 60505530705, 60760065225, 61442011101, 61442011105, 61442011201, 61442011205, 61442011301, 61442011305,
	61442011401, 61442011405, 61919000335, 61919033130, 61919037030, 61919053030, 61919053035, 61919065430, 62332024805, 62332024815, 62332024830, 62682102001, 62682102006,
	62682102102, 62991100401, 62991100402, 62991100403, 62991100404, 62991100405, 63187018290, 63187025315, 63187025330, 63187025360, 63187057406, 63187057425, 63304050401,
	63304050501, 63304065201, 63304065205, 63307001611, 63307001615, 63307001639, 63370000725, 63629167601, 63629167602, 63629167603, 63629167604, 63629167605, 63629167601, 63629167602, 63629167603, 63629167603, 63629167604, 63629167605, 636291
	63629167702, 63629167703, 63629167704, 63629167705, 63629167706, 63629167707, 63629167801, 63629167802, 63629167803, 63629167804, 63629167805, 63646030015, 63646030030,
	63739031410, 63739031415, 63739031510, 63739031515, 63739031610, 63739031615, 63739031615, 63739068210, 63874040401, 63874040410, 63874040414, 63874040415, 63874040412, 63874040424,
	63874040425, 63874040430, 63874040435, 63874040440, 63874040450, 63874040460, 63874040470, 63874040501, 63874040510, 63874040520, 63874040525, 63874040530, 63874040535,
	63874050001, 63874050015, 63874050020, 63874050021, 63874050025, 63874050025, 63874050030, 63874050040, 63874050060, 65162008810, 65162083594, 65162083596, 66116024550, 66116024650,
	66116027135, 66267000625, 66267000640, 66267000650, 66267000715, 66267000721, 66267000725, 66267000730, 66267039930, 66267039935, 66336064225, 66336064220, 66336064240,
	66336064250, 66336073515, 66336073525, 66336073530, 66336073540, 66336073560, 66336086225, 66336086230, 66336086235, 66336086250, 67253010010, 67253010011, 67253010110,
	67253010111, 67253010210, 67253010250, 68030695002, 68084010701, 68084010711, 68084010801, 68084010811, 68084010901, 68084010911, 68115000510, 68115000525, 68115000540,
	68115000610, 68115000615, 68115000621, 68115000625, 68115000630, 68115000630, 68115000606, 68115000730, 68382079101, 68382079105, 68382079201, 68382079205, 68382099201, 68382099204,
	68462074617, 68462074635, 68682099595, 68788050403, 68788050406, 68788050407, 68788050503, 68788050507, 68788050508, 68788636002, 68788636003, 68788636004, 68788636005,
	68788636006, 68788636007, 68788636008, 68788682703, 68788682704, 68788682705, 68788682706, 68788734201, 68788734202, 68788734203, 68788734204, 68788734205, 68788734206,
	68788734207, 68788734208, 68788734209, 68788737802, 68788737803, 68788737804, 68788737805, 68788737806, 68788737807, 68788737808, 68788738202, 68788738203, 68788738204,
	68788738205, 68788738206, 68788738207, 68788738208, 68788898902, 68788898903, 68788898904, 68788898905, 68788898906, 68788898907, 68788898908, 68788969003, 69076014601,
	69117001801, 69117001802, 69117001901, 69117001902, 70457989303, 70457989304, 70934013130, 70934013235, 71092998001, 71092998002, 71092998003, 71092998004, 71092998005,
	71092998006, 71205005330, 71205005335, 71205005630, 7120502950, 71205024390, 71335022500, 71335022501, 71335022502, 71335022503, 71335022504, 71335022505, 71335022506,
	71335022507, 71335022508, 71335022509, 71335024800, 71335024801, 71335024802, 71335024803, 71335024804, 71335024805, 71335024806, 71335024807, 71335024808, 71335024809,
	71335028000, 71335028001, 71335028002, 71335028003, 71335028004, 71335028005, 71335028006, 71335028007, 71335028008, 71335028009, 71335031901, 71335031902, 71335031903,
	71335031904, 71335031905, 71335031906, 71335031907, 71335031908, 71335031909, 71335032300, 71335032301, 71335032302, 71335032303, 71335032304, 71335032305, 71335032306,
	71335032307, 71335032308, 71335032309, 71335047000, 71335047001, 71335047002, 71335047003, 71335047004, 71335047005, 71335047006, 71335047007, 71335047008, 71335047009,
	71335069502, 71335069508, 75834012201, 75834012205, 75834012301, 75834012305, 75834012401, 68712004901, 68712004902, 71403004901, 71403004902, 00173094555, 00173094556,
	00173094955, 00173095396, 00173099155, 00173099156, 00173099341, 00187099395, 00187099445, 00247007500, 00247007506, 00247007506, 00247007520, 00247007525, 00247007530,
	00247007535, 00247007540, 00247007542, 00247007548, 00247007550, 00247007560, 00247016910, 00247016920, 00247016928, 00247016930, 00247016935, 00247016950, 00247016950, 00247016950, 00247016930, 002470000000000000000000000000000000000
	00247033615, 00247033621, 00247033625, 00247033628, 00247033630, 00247033635, 00247068403, 00378973573, 35356024115, 40076094555, 40076094955, 40076095396, 40076099155,
	42254014905, 42254028505, 51655020477, 52959033000, 52959033025, 52959033050, 54348062210, 54348062215, 54348062230, 54569009100, 54569009101, 54569079200, 54569204700,
	54569419200, 54569419201, 54868016301, 54868016302, 54868016303, 54868016304, 54868016306, 54868016501, 54868016502, 54868218400, 54868218402, 54868218403, 54868218404,
	54868302500, 54868541000, 54868541001, 55045130104, 55045185701, 55045185704, 55289000610, 55289000625, 55289000635, 55289000630, 55289056415, 55289056420, 55289056448,
	55289069112, 55289069115, 55289069125, 57866107802, 58016310301, 60346000610, 60346000615, 60346000620, 60346000625, 60346000630, 60346000635, 60346000635, 60346000644, 60346000648,
	60346073525, 64455099394, 64455099395, 64455099442, 64455099445
Acyclovir	00074199010, 00074442701, 00074442749, 00074445201, 00074445249, 55150015410, 55150015411, 55150015520, 55150015521, 55390061210, 55390061320, 61703031121, 61703031143,
Sodium	63323010510, 63323032510, 63323032524, 63323032524, 00173095201, 00173099501, 70004000533
oululli	33555 135 13, 33555555 13, 335555555 13, 335555555 1, 33755555 1, 33755555 1, 33755555 1, 33755555 1, 33755555

## 219111 (EPI-ZOSTER-097 VE US DB) Protocol Final

Drug	NDCs
Acyclovir Susp 200 Mg/5Ml	50962045360, 60346085434, 60346085471
Acyclovir, Micronized	28595059277
Acyclovir/ Hydrocortis one	00037050105, 00187510401
Acyclovir/ Lidocaine Hcl	28595097362
Famciclovir	00054019613, 00054019713, 00054019813, 00093811756, 00093811856, 00093811956, 00378449093, 00378449193, 00378449293, 00440750002, 00440750010, 00440750121, 00440750160, 00440750202, 00440753121, 00591327130, 00591327230, 00591327330, 00781562031, 00781562131, 00781562231, 16714030001, 16714030401, 16714030501, 16714061401, 16714061501, 16714061601, 31722070630, 31722070730, 31722070830, 33342002407, 33342002507, 33342002607, 42291027530, 42291027530, 42291027730, 50090306600, 50090333700, 50268030511, 50268030513, 50268030613, 50268030613, 50268030711, 50268030713, 52959094604, 52959094621, 54569604600, 54569604601, 54868590500, 54868590501, 54868590503, 54868590504, 55289016803, 59762270001, 59762270301, 60429035930, 60429036030, 60429036130, 60505324503, 60505324603, 60505324703, 60687010325, 60687010395, 63187091921, 63187099821, 63187099821, 63187099821, 63187099830, 65862046530, 65862046630, 65862046730, 69097026902, 69097027202, 00078036615, 00078036615, 00078036815, 00078036861, 00078036864, 00440752802, 49999030821, 49999030830, 54348062310, 54569453300, 54569453400, 54569453401, 54569466000, 54868388200, 54868388201, 54868396900, 54868396901, 54868400900, 54868400901, 68115040730, 68115040760, 68115040830, 68115040860, 68115040801, 68115040921, 68115040930, 68115040960
Valacyclovi r Hcl	0054011413, 00054011427, 00054011527, 00093725856, 00093725898, 00093725956, 00093725958, 00378427505, 00378427507, 00378427593, 00378427605, 00378427607, 00378427603, 00591324830, 00591324830, 00591324830, 00781520892, 00781520892, 00781520992, 00904656507, 00904656501, 10544093704, 16714069702, 16714069802, 16714069802, 16714069803, 21695083210, 21695083221, 21695083230, 21695096504, 21695096507, 21695096521, 31722070430, 31722070430, 31722070590, 42254044110, 42291088930, 43063020010, 43063048810, 43063048414, 4306305404, 43063053421, 4306307310, 43063073090, 43063076806, 43063077110, 43063077112, 43063077810, 43063077814, 43063077890, 4335308699, 4335308699, 4335308839, 45963055804, 45963055808, 45963055808, 45963055808, 45963055809, 45963055803, 5090917300, 5009017300, 5009017302, 50090222300, 50090251001, 50090251001, 50090257500, 50090257502, 50090257503, 50268078815, 50268078815, 50268078915, 51079009301, 51079009303, 51660090430, 52434005130, 52343005130, 52343005230, 52343005230, 5234300530, 52343005130, 54669617802, 54668609905, 54668609905, 54668609905, 54668609905, 54668609905, 54668609905, 54668609905, 54668609905, 54668609905, 54668609905, 54668609905, 54668609905, 57237004230, 5723700430, 5723700430, 5

## 219111 (EPI-ZOSTER-097 VE US DB) Protocol Final

Drug	NDCs
	53002078330, 53002078340, 53217005410, 53217005414, 53217005430, 53217005430, 53217005490, 54569617803, 58118090403, 58118090409, 61919006660, 68788637901, 68788637902, 68788637903, 68788637904, 68788637907, 71335002106, 71335070806, 72189003721, 00173056502, 00173056504, 00173056510, 00173093303, 00173093308, 00173093310, 00173093356, 00440860106, 00440860204, 00490005200, 00490005230, 00490005260, 00490005290, 23490704901, 23490704903, 33358035306, 33358035310, 33358035312, 33358035330, 49999048607, 49999048630, 49999086503, 49999086518, 49999086530, 52959038421, 52959064110, 52959064114, 52959064130, 52959064142, 54569428000, 54569428001, 54569428002, 54569428003, 54569428004, 54569428007, 54569532401, 54569532402, 54569532403, 54868380400, 54868380401, 54868380402, 54868380403, 54868380404, 54868380405, 54868399300, 54868399301, 54868399302, 54868399303, 54868399304, 54868399305, 54868399307, 54868399307, 54868399308, 55289092604, 55289092604, 57860126502, 58016085501, 58864068320, 58864068321, 62682101201, 62682101304, 63629398201, 67544006930, 67544006953,

# 13.5. Appendix 5 : Diagnosis codes for co-morbidities

Cardiovascular disease   12.0,   12.9,   13.1*,   N03.2-N03.7,   N05.2-N05.7,   N18.*,   N19.*,   N25.0,   Z49.0*-Z49.2*,   Z94.0,   Z   Cardiovascular disease   121.*,   122.*,   125.2,   109.9,   11.0,   13.0,   13.2,   125.5,   142.0,   142.5-  142.9,   143.*,   150.*,   P29.0   Pulmonary disease   127.8*,   127.9,   140.*-  147.*,   160.*-  167.*,   168.4,   170.1,   170.3   B18.*,   185.0*,   186.4,   198.2,   K70.0,   K70.1*-  K70.4*,   K70.9,   K71.1*,   K71.3,   K71.4,   K71.5*,   K71.7,   K72.1*,   K72.9*,   K73.*,   K74.*,   K76.0,   K76.2-  K76.7,   K76.8*,   K76.9,   Z94.4   Diabetes mellitus   E10.*-E14.*  Autoimmune conditions   Rheumatoid arthritis   M05.*,   M06.*   Inflammatory bowel disease   K50.*,   K51.*   Psoriasis/Psoriatic arthritis   L40.*,   L40.5*	Covariate	ICD-10 codes
Cardiovascular disease   121.*,   122.*,   125.2,   109.9,   111.0,   13.0,   13.2,   125.5,   142.0,   142.5-  142.9,   143.*,   150.*,   150.*,   129.0   Pulmonary disease   127.8*,   127.9,   140.*-  147.*,   160.*-  167.*,   168.4,   170.1,   170.3    Liver disease   181.*,   185.0*,   186.4,   198.2,   187.0,	Chronic diseases	
Pulmonary disease Liver disease Liver disease Diabetes mellitus Diabetes mellitus  Rheumatoid arthritis Rhound disease	Kidney disease	12.0,   12.9,   13.1*, N03.2-N03.7, N05.2-N05.7, N18.*, N19.*, N25.0, Z49.0*-Z49.2*, Z94.0, Z99.2
Liver disease  B18.*, I85.0*, I86.4, I98.2, K70.0, K70.1*-K70.4*, K70.9, K71.1*, K71.3, K71.4, K71.5*, K71.7, K72.1*, K72.1*, K72.9*, K73.*, K74.*, K76.0, K76.2-K76.7, K76.8*, K76.9, Z94.4  Autoimmune conditions  Rheumatoid arthritis  Inflammatory bowel disease  K50.*, K51.*  Psoriasis/Psoriatic arthritis  L40.*, L40.5*	Cardiovascular disease	121.*, 122.*, 125.2, 109.9, 111.0, 113.0, 113.2, 125.5, 142.0, 142.5-142.9, 143.*, 150.*, P29.0
Diabetes mellitus E10.*-E14.*  Autoimmune conditions  Rheumatoid arthritis M05.*, M06.*  Inflammatory bowel disease K50.*, K51.*  Psoriasis/Psoriatic arthritis L40.*, L40.5*	Pulmonary disease	127.8*, I27.9, J40.*-J47.*, J60.*-J67.*, J68.4, J70.1, J70.3
Autoimmune conditions  Rheumatoid arthritis  Inflammatory bowel disease K50.*, K51.*  Psoriasis/Psoriatic arthritis L40.*, L40.5*	Liver disease	B18.*, I85.0*, I86.4, I98.2, K70.0, K70.1*-K70.4*, K70.9, K71.1*, K71.3, K71.4, K71.5*, K71.7, K72.1*, K72.9*, K73.*, K74.*, K76.0, K76.2-K76.7, K76.8*, K76.9, Z94.4
Rheumatoid arthritis M05.*, M06.* Inflammatory bowel disease K50.*, K51.* Psoriasis/Psoriatic arthritis L40.*, L40.5*	Diabetes mellitus	E10.*-E14.*
Inflammatory bowel disease K50.*, K51.* Psoriasis/Psoriatic arthritis L40.*, L40.5*	Autoimmune conditions	
Psoriasis/Psoriatic arthritis L40.*, L40.5*	Rheumatoid arthritis	M05.*, M06.*
	Inflammatory bowel disease	K50.*, K51.*
	Psoriasis/Psoriatic arthritis	L40.*, L40.5*
Multiple sclerosis G35	Multiple sclerosis	G35
Systemic lupus erythematosus M32.1, M32.8, M32.9	Systemic lupus erythematosus	M32.1, M32.8, M32.9

Immunosuppressant conditions

Lymphoma/leukemia C81.\*C86.\*, C88.\*, C90.\*-C96.\*, D45, D46.\*

Congenital and other D61.09, D61.3, D61.82, D61.9, D70.0, D71, D80.0, D80.1, D80.5, D80.8, D81.\*, D82.\*, D83.\*, immunodeficiencies D84.0, D84.1, D84.89, D84.9, D89.81\*, D89.82, D89.9, E31.0, E70.330, G11.3, Q82.4, Q89.0\*

D57.00, D57.01, D57.02, D57.1, D57.2, D57.20, D57.21, D57.211, D57.212, D57.219, D57.4, Asplenia/hyposplenia D57.40, D57.411, D57.411, D57.412, D57.419, D57.8, D57.80, D57.81, D57.811, D57.812, D57.819, D73.0, Q89.01, Q89.09, Z90.81

	COVID-19 virus identified (On February 11, 2020, the WHO announced the official name of COVID-19)
J12.82	Pneumonia due to coronavirus disease 2019

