Presence of co-morbidities: kidney disease, cardiovascular disease, pulmonary disease [i.e., chronic obstructive pulmonary disease or chronic bronchitis, asthma], liver disease, diabetes mellitus, other autoimmune diseases, cancer, immunocompromising conditions [i.e., human immunodeficiency virus, cancer, transplant, immune-suppressive medications], SARS-CoV-2 infection/COVID-19 diagnosis with an index date after 2020) in the 365 days prior to the index date [Kawai, 2017a; Marra, 2020; Tsai, 2017; Yun, 2016].

Concomitant vaccinations during baseline: Influenza vaccine, tetanus, diphtheria and pertussis vaccine, pneumococcal vaccine in the 365 days prior to the index date, as a proxy for health behaviors.

Region of residence within U.S. as defined by the Census Bureau (4 regions: West, Midwest, South, Northeast) most recently prior to the index date [Izurieta, 2021; Sun, 2021].

Use of preventative services: screening, preventative visits in the 365 days prior to the index date [Izurieta, 2021].

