### 7. STUDY POPULATION

## 7.1. Description of population

The study population will include adults aged ≥50 YOA who are beneficiaries in the OptumTM database, diagnosed with an AID (defined as RA, IBD [UC or CD], SLE, PsO, PsA and MS), and who received RZV vaccination (along with their unvaccinated matches) anytime between 1 January 2018 to 31 December 2021 (Section 7.5 describes the algorithms for identification of AIDs). Co-existence of more than one AID can occur – while it is not required that each AID cohorts be mutually exclusive, overlap is expected to be minimal. Details of inclusion and exclusion criteria are defined in Sections 7.2 and 7.3.

Table 1 shows the demographic characteristics of beneficiaries in the OptumTM database diagnosed with RA, IBD, SLE, PsO, PsA and MS during the study period (2018-2021) based on the inclusion criteria (Section 7.2) and exclusion criteria (Section 7.3). Most of the beneficiaries with SLE (38.6%), PsA (38.9%), and MS (47.3%) were 50-59 YOA, while most of the participants with IBD (39.4%), RA (42.8%), and PsO (36.9%) were

219111 (EPI-ZOSTER-097 VE US DB)
Protocol Final

>70 YOA. Most of these beneficiaries were female while over 60% were white in all AID groups.

Table 1 Demographic characteristics of beneficiaries by AID condition\* during the study period (2018^-2021).

	SLE		IBD		RA		PsO		PsA		MS	
	N	%	N	%	N	%	N	%	N	%	N	%
Age at AID diagnosis (years)												
50-59												47.
	7740	38.6	11254	34.4	32130	30.5	22794	35.5	6194	38.9	10150	3
60-69												31.
	6086	30.4	8577	26.2	28028	26.6	17668	27.5	4968	31.2	6828	8
≥70												20.
	6224	31	12875	39.4	45029	42.8	23680	36.9	4747	29.8	4463	8
Sex												
Female												76.
	17665	88.1	18690	57.1	79127	75.2	34772	54.2	9314	58.5	16431	6
Male												23.
	2385	11.9	14016	42.9	26060	24.8	29370	45.8	6595	41.5	5010	4
Race /Ethnicity	1											
Asian	446	2.2	593	1.8	2331	2.2	1853	2.9	342	2.1	208	1
Black												10.
	3824	19.1	2796	8.5	13609	12.9	4440	6.9	930	5.8	2290	7
Hispanic	2492	12.4	2296	7	13491	12.8	5530	8.6	1505	9.5	1262	5.9
Multiple/Other/												
Unknown	1076	5.4	1529	4.7	5299	5	2944	4.6	760	4.8	972	4.5
White												77.
	12212	60.9	25492	77.9	70457	67	49375	77	12372	77.8	16709	9
Total	20050	-	32706	-	105187	-	64142	-	15909	-	21441	-

\*Table presents overall distribution of beneficiaries' characteristics by AID; no information on vaccination status (see Table 3).

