#### PsO:

 $\geq$ 1 inpatient claim with a diagnosis code for PsO (ICD-10 L40) OR  $\geq$ 2 physician outpatient claims with PsO diagnosis during an office visit and/or emergency visit that were at least 30 days apart OR  $\geq$ 1 dermatologist visit/encounter/claim for PsO in the 365-day baseline period prior to the index date.

• The algorithm that includes ≥1 dermatologist visit/encounter/claim has demonstrated a PPV of 90% and sensitivity of 88% [Asgari, 2013]. These algorithms assume PsO without PsA. Based on the rapid data queries (RDQs), 9% of participants diagnosed with PsO had PsA. In practice, rheumatologists tend to assess PsO and PsA by criteria which are unique to each. Then, they assess the 2 AIDs together in patients with symptoms of both. Sensitivity analyses will be performed on participants who

219111 (EPI-ZOSTER-097 VE US DB) Protocol Final

have either PsO or PSA, participants who have PsO only, participants who have PsA only, and participants who have both PsO and PsA to address the potential overlap between PsO and PsA. These analyses will be described in detail in the SAP.

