#### PsA:

 $\geq$ 1 inpatient claim with a diagnosis code for PsA (ICD-10 L40.5) OR  $\geq$ 2 physician outpatient claims with PsA diagnosis during an office visit and/or emergency visit that were at least 30 days apart OR  $\geq$ 2 rheumatologist visit/encounter/claim for PsA OR  $\geq$ 1 rheumatologist diagnosis code for PsA together with  $\geq$ 1 dermatologist diagnosis code for PsA in the 365-day baseline period prior to the index date.

• The algorithm that includes ≥2 rheumatologist visit/encounter/claim for PsA has demonstrated a PPV of 81% and sensitivity of 77% [Asgari, 2013]. These algorithms assume PsA without PsO. Based on the RDQs, 37% of participants diagnosed with PsA had PsO. Sensitivity analyses will be conducted to address the potential overlap between PsO and PsA as described above.

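### Appendix 5 codes psoriasis and psoriatic arthritis in one row, so the PsO and PsA propensity scores have no direct term for coexistence of the two diseases

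*Protocol*

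**What the plan says.** Protocol Section 6.3 lists the co-morbidities measured in the 365 days before index, including "other autoimmune diseases, cancer, immunocompromising conditions". Section 7.6 puts the listed covariates into a logistic propensity model fitted within each AID cohort. It then checks balance by standardized differences, with 0.2 as the mark of important imbalance. A covariate still imbalanced is added to the Cox model.

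Appendix 5 (Section 13.5) supplies the codes. RA, IBD, MS and SLE each have their own row. Psoriasis and psoriatic arthritis share one: "Psoriasis/Psoriatic arthritis L40.*, L40.5".

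Cohort entry in Section 7.5 uses the same code family over the same baseline year. For PsO the codes appear as "inpatient claim with a diagnosis code for PsO (ICD-10 L40", with outpatient and dermatologist alternatives. For PsA they appear as "inpatient claim with a diagnosis code for PsA (ICD-10 L40.5", with outpatient and specialist alternatives.

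On overlap, Section 7.1 says generally that "overlap is expected to be minimal". Section 7.5 then reports that "9% of participants diagnosed with PsO had PsA" and that "37% of participants diagnosed with PsA had PsO". Sections 7.5 and 11.3.5 plan sensitivity analyses in participants with either disease, PsO only, PsA only, and both.

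**The concern.** A covariate that takes the same value for everyone in a cohort drops out of the propensity model and always shows a standardized difference of zero. Reading the covariate as excluding the cohort's own disease does not help here. For RA, IBD, MS or SLE the own row can go and every other disease remains. For PsO and PsA the row is shared, so removing it also removes the companion disease.

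PsO and PsA are primary objectives 5 and 6, and the crude HZ rates in Table 2 differ between them. If vaccinated and unvaccinated PsO participants differ in how many also have PsA, the primary model has no term for it. The rule that moves an imbalanced covariate into the Cox model could not be triggered by it either.

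**Working it through.** **1. The overlap figures.** Inputs: 9% and 37% (Section 7.5); 64,142 PsO and 15,909 PsA beneficiaries (Table 1).
- 0.09 × 64,142 = 5,773
- 0.37 × 15,909 = 5,886, and 5,886 / 64,142 = 9.2%

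The two percentages agree. If any `L40.*` code, including `L40.5*`, had counted as PsO, every PsA patient would have had PsO (100%, not 37%), and PsA would have been 15,909 / 64,142 = 24.8% of PsO, not 9%. The rapid data queries evidently told the diseases apart.

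**2. The code logic.** `L40.5*` lies inside `L40.*`. PsO entry needs L40 and PsA entry needs L40.5, both in the baseline year. The Appendix 5 row is therefore 1 for everyone in either cohort: prevalence 100%, variance 0. With separate flags, PsA in the PsO cohort would have prevalence about 9% (variance 0.09 × 0.91 = 0.08), and psoriasis in the PsA cohort about 37% (0.37 × 0.63 = 0.23). Both could then be modelled and checked.

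**3. Whether another covariate fills the gap.** Section 6.3 lists rheumatologist visits for SLE, RA and PsA, but not PsO. It lists dermatologist visits for SLE and PsO, but not PsA. Neither cohort gets the visit count that would point most directly to the companion disease.

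**4. Rates.** From Table 2:
- PsO: 1,533 / 134,443 = 11.40 per 1000 PY
- PsA: 499 / 34,023 = 14.67 per 1000 PY

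Both match the printed values. Assume PsO patients with PsA have the PsA cohort's rate:
- PsO without PsA = (11.40 − 0.09 × 14.67) / 0.91 = 11.08
- rate ratio = 14.67 / 11.08 = 1.324

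**5. Possible bias, PsO cohort.** With prevalence p_v in vaccinated and p_u in unvaccinated participants, the HR is multiplied by (1 + 0.324 p_v) / (1 + 0.324 p_u). The prevalences are assumptions. True VE is taken as 50%.

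| p_v vs p_u | Factor | VE reads | Standardized difference |
|---|---|---|---|
| 14% vs 9% | 1.016 | 49.2% | 0.16 |
| 4% vs 9% | 0.984 | 50.8% | 0.20 |
| 20% vs 5% | 1.048 | 47.6% | 0.47 |

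The standardized difference is |p_v − p_u| / √{[p_v(1 − p_v) + p_u(1 − p_u)] / 2}. If the rate ratio were 2, the 5-point imbalances would give 47.7% to 52.3%.

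**6. Possible bias, PsA cohort.** Table 2 gives no rate for PsA with and without psoriasis, so any ratio here is an assumption. With 1.32 and a 10-point imbalance (47% or 27% vs 37%), VE reads 48.6% to 51.4%. With a ratio of 2 it reads 46.4% to 53.6%.

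**The case against.** The strongest reply is that the row is shorthand. Its two codes follow the order of its label, the second would be redundant if one wildcard were meant, and Appendix 4 lists PsO and PsA on separate lines. The rapid data queries separated the diseases. Appendix 5 does not say whether its autoimmune rows enter as one composite or as separate indicators, and Section 7.6 leaves propensity-score details to the SAP, which is not at hand. This makes it plausible that the programmers would separate the diseases. It does not change what the protocol prints, which a SAP following it would inherit.

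Second, proxies exist. Matching is exact on AID medication category, and baseline medications, visits, admissions and cost enter the model. Section 3 says HZ risk in PsO and PsA depends on severity and type of systemic therapy, so part of the crude rate gap may be matched away. That stands, but the proxies are partial, and the PsO and PsA medication categories are still to be written (13.6.4.1 and 13.6.4.2).

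Third, the overlap has its own sensitivity analyses. In the PsO-only analysis PsA is absent by restriction, so a problem could show there. That lowers the weight of the point but leaves the primary estimates as they are.

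Fourth, the shift is small beside sampling error. Using Tables 2 and 3, VE 50%, 3:1 matching and independent controls, PsO expects about 12,086 × 1.4 × 0.0114 × 0.5 = 96 vaccinated and 3 × 12,086 × 1.4 × 0.0114 = 579 unvaccinated events. That gives a 95% CI of roughly 38% to 60%. A 5-point imbalance at 14% vs 9% would also fall below the plan's 0.2 mark. Both points stand.

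**Conclusion.** The point holds as a specification gap of small expected size. As printed, the Appendix 5 row says nothing about whether a PsO participant also has PsA, or the reverse, and no other listed covariate measures this directly. Under a rate ratio of 1.32 taken from crude Table 2 rates, the assumed PsO imbalances move a VE of 50% by 0.8 points (5-point imbalance) to 2.4 points (an extreme 15-point one). The direction is unknown. The loss of the balance check matters at least as much: an imbalance with a standardized difference of 0.47 would not appear on this covariate.

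Three stronger readings are tempting, and the protocol does not support them:
- **The whole autoimmune covariate is 1 for everyone.** This is true of the psoriatic row only. The RA, IBD, MS and SLE rows still vary if entered separately, and the protocol does not say that they are collapsed.
- **The propensity score cannot balance the overlap.** It has no direct term, but medication matching and utilisation may balance it in part.
- **This is the largest AID overlap in the study.** It is the only one with a figure; no other pair is quantified, so no ranking is possible.

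Nor do the figures support a claim that primary objectives 5 and 6 are materially biased.

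**What to change.** In Appendix 5, replace the merged row with two:
- Psoriasis: `L40.*` except `L40.5*`
- Psoriatic arthritis: `L40.5*`

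The exclusion is needed. Without it, the psoriasis flag would again be 1 for everyone in the PsA cohort.

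In Section 6.3, state that coexisting autoimmune disease enters as a separate flag for each listed AID other than the cohort's own. The PsA flag then enters the propensity score and balance table of the PsO cohort, and the non-L40.5 psoriasis flag enters those of the PsA cohort.

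The cost is one edited row and one clause. The codes are already extracted for cohort entry, so no new data are needed, and the planned sensitivity analyses can stay as they are.
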